## 1 SCHEDULE OF STUDY VISITS AND PROCEDURES

2 This is a remote study design with virtual visits; eligibility and other study questionnaires are by participant self-report.

3

	Enrollment	Initial Virtual Clinic Contact	Baseline CGM Data Collection	Virtual Clinic Training Phase (0-13 Weeks)					Virtual Clinic Follow Up Phase	Optional Extended Participant Follow Up	
				Training 1 (Week 0)	Training 2 (Week 1)	Training 3 (Week 3)	CGM Follow Up (Weeks 4, 8)	CGM Follow Up (Week 13)			
TARGET WINDOW		Within 7 Days from Completion of Enrollment Questionnaires		Day 0	Day 7-14	Day 21-28			Weeks 12-14		
ICF • Eligibility Confirmation	X									X*	X*
Baseline Data Collection • Contact Information • Demographics • Medical History • Questionnaires	X		X								
Follow-Up Data Collection**					X	X	X	X	X	X	X
HbA1c***			X					X	X	X	X
Video Tutorials / Access to Resource Materials		Examples: CGM Overview Parts of CGM	Examples: HbA1c Sample Collection CGM Setup	Examples: Understanding Your Real-Time Data How to Change Sensor	Examples: How to Upload CGM Data How to View Reports Understanding Your Ambulatory Glucose Profile / Data Patterns	X	X	X	X	X	X
Contact with Study Team†		X	X	CGM Initiation	CGM Data Interpretation	CGM Data Review Goal Setting	X	X	X	X	X
CGM Use††			~2 Week Blinded CGM Use †††	Start of 26-Week Unblinded CGM Use	X	X	X	X	X	X	X

\*. Participants will be asked to extend follow up for an additional 26 weeks and sign an addendum ICF if they plan to continue to use CGM after the first 26 weeks. Virtual Clinic follow up will be available to participants on an as-needed basis after the first 26 weeks.

\*\*Participants will be asked to complete questionnaires monthly after CGM Initiation. A final questionnaire will be elicited at the earlier of CGM discontinuation or completion of study follow up (~52 weeks).

\*\*\*HbA1c checks prior to unblinded CGM initiation, and at 3-month intervals following CGM initiation (~13 weeks, 26 weeks, 39 weeks, and 52 weeks)

†Follow up may be via phone, text, virtual (i.e. Skype), or app. outside of scheduled training. Additional follow up may be conducted as needed. Participants may follow up with study team as needed.

††CGM supplied for blinded data collection will be provided. CGM supplies for six months of unblinded use will be provided for those who successfully complete blinded data collection.

†††Current CGM users are not required to wear blinded CGM unless current CGM data cannot be shared to establish baseline.

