112 document, with the ethical principles that have their origin in the Declaration of Helsinki, with  
113 the protocol described herein, and with the standards of Good Clinical Practice (GCP).

114 **Chapter 2: Study Enrollment and Baseline Data Collection**

115 **2.1 Participant Recruitment and Informed Consent**

116 Adults (age  $\geq 18$  years) with type 1 diabetes or type 2 diabetes using insulin therapy (Tidepool-  
117 compatible pump or injections) will be enrolled. Although the primary focus of the study is to  
118 enroll non-CGM users, CGM users whose glycemic control is suboptimal can be enrolled.  
119 Participation will be limited to U.S. residents in states where the virtual clinic is licensed; state  
120 eligibility will be verified as part of screening. Potential participants may be recruited through  
121 insurance providers, primary care networks, or health care providers. Potential participants also  
122 may become aware of the study by other means, such as another study participant.

123 Up to 800 individuals may sign the informed consent form to initiate screening. Enrollment will  
124 proceed with the goal of at least 300 participants initiating training for CGM use with the Virtual  
125 Clinic. The goal will be to limit T2D enrollment to no more than 100. Recruitment efforts will be  
126 focused on participants who receive diabetes care in a primary care setting rather than through an  
127 endocrinologist, with a goal of having at least 225 who have not seen an endocrinologist in the  
128 past six months. Eligible participants will be included without regard to gender, race, or  
129 ethnicity.

130 The goal will be to include at least 50 participants  $<25$  years of age and at least 50 participants  
131  $>65$  years of age.

132 **2.1.1 Informed Consent and Authorization Procedures**

133 Individuals who indicate that they are interested will be directed to a website with information  
134 about the study. Interested individuals will be able to communicate with study staff who can  
135 answer questions about the study as part of the informed consent process. Individuals who want  
136 to participate in the study will sign the Institutional Review Board (IRB) approved electronic  
137 consent form. As part of the informed consent process, each participant will be asked to sign an  
138 authorization for release of personal information. Participants will be asked to sign an addendum  

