173 9. Participation in a different diabetes management study during the study  
174 10. Planned relocation to a state other than current state of residence during the study if virtual  
175 clinic is not licensed in the new state.

176 *Individuals working routinely in a state other than current state of residence in the next six  
177 months are also ineligible if the virtual clinic is not licensed in that state.*

178 **2.4 Screening Procedures**

179 Participants will be asked to confirm eligibility by completing a screening questionnaire.  
180 Participants who pass screening will be asked to provide baseline data. Current CGM users will  
181 also be asked to share their CGM data to confirm eligibility. If current data cannot be shared,  
182 current CGM users will be asked to complete blinded CGM data collection. Non-CGM users  
183 will also be asked to complete blinded CGM data collection. Participants will be asked to submit  
184 a baseline HbA1c sample

185 **2.5 Collection of Baseline Data and Testing**

186 After informed consent is signed, baseline data will be collected, including the following:

187 • Contact information  
188 • Date of birth

189 • Demographics  
190 • Height and weight  
191 • Socio-economic information such as education, income, and insurance  
192 • Name and contact information of healthcare provider for diabetes management  
193 • Diabetes history, including diabetes duration, prior management, insulin delivery method,  
194 meal bolus determination method, prior severe hypoglycemia (SH), prior diabetic  
195 ketoacidosis (DKA)  
196 • Medical history  
197 • Medications, including but not limited to medications other than insulin being used for  
198 glycemic control  
199 • Prior CGM experience and knowledge, including why CGM is not used  
200 • General health  
201 • Questionnaires (see Chapter 4)  
202 • Finger stick to measure HbA1c  
203 • Blinded CGM Data Collection

204 **2.5.1 HbA1c**

205 HbA1c will be measured at a central laboratory. The participant will be sent a kit, which will  
206 include a blood collection tube and shipping materials, to obtain a finger stick blood sample. The  
207 sample will be returned to the lab in a prepaid mailer. Participants will be able to view their  
208 HbA1c results through the study website.

209 **2.6 CGM System**

210 Participants will use the Dexcom G6, which is a commercially available CGM system. CGM  
211 data will be shared with CDCES and study team members.

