314 Data will be collected throughout study follow up and will include information related to  
315 diabetes management, psychosocial outcomes, adverse event and device issues, patient-related  
316 outcomes and questionnaires, HbA1c measurement, and upload of device data.

317 **3.6.1 HbA1c**

318 HbA1c will be collected at approximately 13, 26, 39, and 52 weeks and measured at a central  
319 laboratory. A kit, which will include a blood collection tube and shipping materials, will be sent  
320 to the participant to obtain a fingerstick blood sample and return the sample to the lab.

321 **3.7 Data Uploads**

322 Instructions for downloads and data sharing from diabetes-related care devices and applications  
323 used for the study will be reviewed with each participant as part of their training.

324 **3.8 Insulin Delivery and Collection of Insulin Data**

325 Participants will use their own insulin during the study. If the participant uses an insulin pump,  
326 training will include uploading (or linking) of these devices.

327 MDI users with a compatible insulin pen may be given a Biocorp Mallya (Mallya) device to use  
328 during the study that automatically logs insulin dose. Mallya is a data collection device that  
329 automatically captures data such as date of injection, time of injection, insulin type, and dose.  
330 Mallya attaches directly to the insulin pen and does not alter how the pen is used. Mallya is  
331 intended for data collection purposes only, with minimal information communicated to the  
332 participant via the app or device. Mallya is an investigational device, and it is classified as a  
333 Non-Significant Risk device by the Sponsor.

334 An app that is needed to transfer data from the device used to log insulin dose will be installed  
335 on the participant's personal smartphone. Participants will be trained on use of the device and  
336 app as needed. If a device that automatically logs insulin dose is not available, the participant  
337 may be asked to enter insulin doses directly through an app.

338

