## 344 Chapter 5: Miscellaneous Considerations

### 345 5.1 Adverse Events

346 Participants will be asked to complete questionnaires to report events that have occurred. For  
347 each event reported, the participant will be asked if the event could have been related to the use  
348 of CGM.

349 If there is no response, the participant may be contacted again to encourage questionnaire  
350 completion.

351 Participants will be asked to report the following events:

- 352 • Severe hypoglycemia
  - 353 ○ Reportable events will be defined as hypoglycemia during which the participant was  
354 impaired cognitively to the point that he/she was unable to treat himself/herself, was  
355 unable to verbalize his/her needs, was incoherent, disoriented, and/or combative, or  
356 experienced seizure or loss of consciousness.
- 357 • DKA
  - 358 ○ The participant will be asked if he/she was seen at a health care facility and/or  
359 hospitalized and what the ketone level was if known.
- 360 • Hospitalizations

361 Adverse event data reported to virtual clinic team members and study staff will be collected.

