### 452      **6.5 Analysis of Efficacy Outcomes**

453      CGM metrics and HbA1c will be calculated and summarized at 13, 26, 39, and 52 weeks.  
454      Summary statistics for questionnaires will be provided at all time points when they are collected.

455 A linear mixed model with a random subject effect will be used to assess whether the change  
456 from baseline significantly differs from zero. If values are highly skewed, then the winsorized  
457 mean will be tested or a transformation utilized. A complete-case analysis using a paired t-test or  
458 Wilcoxon signed rank test will also be assessed.

459 **6.6 Subgroup Analyses**

460 Subgroup analyses for HbA1c and selected CGM outcomes will be performed by baseline  
461 HbA1c group, insulin delivery modality, age, healthcare provider (endocrinologist or primary  
462 care provider), and various participant characteristics as described in the SAP.

463 **6.7 Safety Analyses**

464 All adverse events that occur post enrollment will be listed in a table. Additionally, each of the  
465 following safety metrics will be tabulated for reported SH and DKA events, hospitalizations and  
466 emergency room visits:

467     • Number of subjects with  $\geq 1$  event  
468     • Number of events per subject  
469     • Incidence rate per 100 person-years

470 **6.8 Baseline Descriptive Statistics**

471 Baseline demographic and clinical characteristics of the cohort of all subjects who initiate the  
472 CGM will be summarized in a table.

473 **6.9 Multiple Comparisons/Multiplicity**

474 No adjustments for multiple comparisons will be made.

475 **6.10 Additional Analyses**

476 Several additional analyses will be performed in this study. These will include the following:

477     • Tabulations of CGM glycemia and CGM use by month and comparing the first 26 weeks  
478 and last 26 weeks of the study (overall and within subgroups)  
479     • Tabulations of CGM glycemia by time of day  
480     • Tabulations of the number of participant contacts with the virtual clinic  
481     • Bivariate relationship between questionnaires and glycemic metrics following CGM  
482 initiation

483 **Chapter 7: Ethics/Protection of Human Participants**

484 **7.1 Ethical Standard**

485 The investigator will ensure that this study is conducted in full conformity with Regulations for  
486 the Protection of Human Participants of Research codified in 45 CFR Part 46, 21 CFR Part 50,  
487 21 CFR Part 56, and/or the ICH E6.

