7.4 Statistical Methods

For all outcomes, summary statistics appropriate to the distribution will be tabulated on a subject level overall and within the subgroups defined in Section 12. For the CGM metrics, summary statistics appropriate to the distribution also will be tabulated for each 4-week interval and for the first and last 26 weeks of the study. For the questionnaires, summary statistics will be reported for the mean scores in addition to the individual responses for each question.

For all outcomes, a linear mixed model with a random subject effect will be used to test whether the mean change from baseline significantly differs from zero. These models will be fit for each of the subject level CGM metrics and HbA1c at 13, 26, 39, and 52 weeks. They also will be fit for the questionnaires at 26 and 52 weeks. If values are skewed, then winsorization will be utilized. Point estimates and 95% confidence intervals for change in glycemic outcomes will be reported.

For the three mental health screening questionnaires, only summary statistics will be tabulated. The three mental health screening questionnaires falling under this umbrella are the Patient

187 Health Questionnaire-8, the Diabetes Distress Scale (Management Distress Subscale), and the
188 Fear of Hypoglycemia Survey (Worry Subscale).

189 **7.5 Analyses Windows**

190 For HbA1c, only measurements occurring within ± 45 days of the target measurement date at a
191 given time point will be included in the tabulation of summary statistics. The windows for
192 glycemic metrics were defined above in Section 7.1.

193 **7.6 Sensitivity Analyses**

194 For CGM and HbA1c outcomes, a complete-case analysis restricting to non-missing outcomes
195 will also be assessed. A paired t-test (for normally distributed outcomes) or a Wilcoxon signed
196 rank test (for skewed outcomes) will be used.

197 **8 Safety Analyses**

198 All adverse events that occur on or after the date of enrollment will be listed in a table.

199 For events occurring on or after the date of CGM initiation, the reported safety outcomes include
200 diabetic ketoacidosis (DKA), severe hypoglycemia (SH), hospitalization, and emergency room
201 visits. The following statistics will be tabulated for each safety outcome:

- 202 • Total number of events
- 203 • Number and proportion of subjects with an event (discretized into bins)
- 204 • Incidence rate per 100 person years

205

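### No adverse-event question is scheduled between enrollment and CGM initiation, or clearly for enrollees who never initiate, although the adverse-event listing runs from enrollment

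*Protocol*

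**What the plan says.** **How events are obtained.** Protocol 5.1 relies on participant self-report: "Participants will be asked to complete questionnaires to report events that have occurred". It names severe hypoglycemia (SH), DKA and hospitalizations. It adds a second route with no stated start date: "Adverse event data reported to virtual clinic team members and study staff will be collected". Protocol 5.2 adds device issues, including skin reactions that are severe or needed treatment.

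**When they are asked about.** Protocol 3.6 places these data in follow-up collection, whose items include "diabetes management, psychosocial outcomes, adverse event and device issues, patient-related". In the Schedule of Study Visits and Procedures, the Follow-Up Data Collection row is first marked at Training 2 (Week 1). Its footnote reads "Participants will be asked to complete questionnaires monthly after CGM Initiation". SAP Table 2 has the same row and footnote. Baseline collection (Protocol 2.5) covers history only; its diabetes-history item includes "meal bolus determination method, prior severe hypoglycemia (SH), prior diabetic" ketoacidosis.

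**What is to be reported.** Protocol 6.7: "All adverse events that occur post enrollment will be listed in a table". SAP 8: "All adverse events that occur on or after the date of enrollment will be listed in a table". Protocol 6.4.1 and SAP 6.1 both include all enrolled participants in safety. SAP 8 then tabulates SH, DKA, hospitalizations and emergency room visits, with incidence rates, only from the CGM initiation date.

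**Who is in the interval.** Protocol 2.1: "Up to 800 individuals may sign the informed consent form to initiate screening". The goal is at least 300 who start CGM training.

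**The concern.** The listing opens at enrollment, but the first scheduled occasion to ask about events comes after CGM initiation. In between lie the first contact, the mailings and, for non-users of CGM, the blinded sensor wear, which is their first exposure to the device in this study.

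The gap is widest for people who enroll and never initiate. They reach no monthly questionnaire. The final questionnaire is triggered by stopping CGM or completing follow-up, and neither clearly describes someone who never started. The loss could also be selective. Under Protocol 2.7, a serious skin reaction during blinded wear that rules out further sensor use leads to being dropped, so such a person leaves before any scheduled event question.

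If solicited and unsolicited periods appear together in one table, a small number of run-in events could be taken as evidence of a quiet run-in when few people were asked.

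**Working it through.** The plan gives no figure to reproduce: the sample is a convenience sample and neither document states an event rate. The check is therefore a comparison of the passages, followed by a rough size.

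**Routes by which an event before initiation could be recorded**

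| Route | Where | What it covers |
|---|---|---|
| Monthly follow-up questionnaire | Protocol 5.1, 3.6, schedule | Starts after initiation. No recall period is stated, so the first could reach back to enrollment, for initiators only |
| Baseline history | Protocol 2.5, schedule | Prior SH and DKA. The row is marked at Enrollment and again at Baseline CGM Data Collection, but no item asks about events since enrollment |
| Reports to staff | Protocol 5.1 | Volunteered. Staff contact is scheduled before initiation, but nothing tells staff to ask about events |
| Skin reactions in blinded wear | Protocol 2.3, 2.7 | Those that rule out continued use must be identified. SH, DKA and hospitalization have no such trigger |
| Withdrawal questionnaires | Protocol 5.5 | Content not stated. Unclear whether people dropped before initiation receive them |

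No row is a scheduled question about events since enrollment, and only the last three could serve a person who is dropped before initiation.

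**Size of the interval**

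Inputs from the documents: 300 initiators and up to 800 consenters (Protocol 2.1), first contact within 7 days of completing the enrollment questionnaires, and about 2 weeks of blinded wear (schedule). The last two sum to about 21 days.

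Assumptions: 14 to 28 days from consent to initiation, since neither document gives this interval, and every consenter counted as enrolled.

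Person-years = n × days / 365.25.

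- 300 initiators: 300 × 14 / 365.25 = 11.5; 300 × 28 / 365.25 = 23.0.
- Up to 500 non-initiators (800 − 300): 500 × 14 / 365.25 = 19.2; 500 × 28 / 365.25 = 38.3.
- All 800: 800 × 14 / 365.25 = 30.7; 800 × 28 / 365.25 = 61.3.

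For comparison, 300 initiators followed in full contribute 300 × 182 / 365.25 = 149.5 person-years over 26 weeks, or 300 × 364 / 365.25 = 299.0 over 52 weeks. Among initiators, time with no scheduled question is then 11.5 / (11.5 + 299.0) = 4% to 23.0 / (23.0 + 149.5) = 13% of exposure since enrollment.

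**Illustrative event count.** An SH count needs a rate that the documents do not give. At an assumed 5 to 20 per 100 person-years, the events occurring in the interval would be 11.5 × 0.05 = 0.6 to 23.0 × 0.20 = 4.6 for initiators. The ceiling for all 800 would be 30.7 × 0.05 = 1.5 to 61.3 × 0.20 = 12.3. These are events that occur, not events missed; some would be volunteered or recalled.

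**The case against.** The strongest reply is that a schedule without a question does not show that nobody asks. Protocol 5.1 sets no recall limit, and the first follow-up mark, Training 2, falls only 7 to 14 days after initiation, so that questionnaire could cover the whole run-in for initiators. Questionnaire procedures are in a manual outside these documents. Baseline history is taken after consent, staff are in contact before initiation and record what they are told, and the skin reactions that matter most must be found for the drop rule to work. All of this stands. A reader might infer that run-in events are never asked about and that the listing is bound to be incomplete; the documents do not support that. They support only that no such question is described. The reply does not reach enrollees who never initiate, because a generous recall period does not help someone who receives no questionnaire.

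A second reply is that the consequence is small. The SAP counts events and person-time for its rates from the same start, CGM initiation. Inferring that those rates are biased by this gap would therefore be wrong; what is exposed is a descriptive listing in an exploratory study. This also stands, although Protocol 6.7 gives no start at initiation for its own tabulations.

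A third reply is that the size is generous. Current CGM users who share their data skip the blinded wear, many of the 800 may leave early in screening, and the all-consenter figures are ceilings. That is correct. In the other direction, a repeated sensor wear would lengthen the interval.

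**Conclusion.** The mismatch is real and modest. Both documents list adverse events from enrollment in all enrolled participants, but neither describes a scheduled event question before CGM initiation or, clearly, for those who never initiate. The part of the listing before initiation may be under-ascertained, most plausibly for people dropped during the run-in. The time at issue is about 11.5 to 23.0 person-years for 300 initiators, and at most 30.7 to 61.3 for 800 consenters. Both ranges rest on the assumed 14 to 28 days, and the second also on every consenter staying that long.

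A reader might go further and say that the study forgoes a solicited event rate before initiation to set against the later one. The documents propose no such comparison, and the illustrative counts would be too few for a useful rate. The case for a change rests on the listing alone.

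**What to change.** 1. Add the Protocol 5.1 and 5.2 event items at Training 1 (Day 0), covering the time since consent, and mark that column in the Follow-Up Data Collection row. Alternatively, state that the recall period of the first follow-up questionnaire starts at consent.
2. Put the same items in the closing or withdrawal questionnaire for anyone dropped before initiation, and say in Protocol 5.5 that these people receive it. This step is needed whichever option is chosen in step 1.
3. In SAP 8, show listed events separately for enrollment to initiation and after initiation, with the number of participants who answered the event items in each period.

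The cost is a few items on the existing study website, about a minute of participant time, a few more listed events and short edits to the protocol and SAP. If collection can no longer be changed, SAP 8 should at least state that events before initiation rest on unsolicited reports, and give the recall period that was used.
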